5.9 Time-To-Event Kaplan-Meier Analysis

The Kaplan-Meier product-limit method will be used to estimate event or event-free rates for time-to-event outcomes as post-hoc analyses.

5.9.1 Kaplan-Meier for Primary Patency

The Kaplan-Meier analysis is aimed to capture the first event for each subject. There are two ways to determine the first event, whichever comes first.

- Clinically-driven TLR date by CEC
- Ultrasound date to identify a subject not patent (i.e. PSVR>2.4)

5.9.2 Kaplan-Meier for MAE-Free

The Kaplan-Meier analysis will capture the first event for MAE-free composite endpoint and/or for selected individual components.

5.10 Time to CEC Adjudicated Events and Time to Adequate Follow-Up

The MAE binary rates (overall and individual components), as opposed to Kaplan-Meier rates, will be calculated based on the subjects who have adequate follow-up and/or have experienced any components of MAE.

The protocol-defined MAEs include:

- all causes of death
- target limb unplanned major amputation
- TLR

5.10.1 Event Rates Presented Using “Month” System

The denominator will be based on number of subjects who reach the protocol-defined lower window (i.e. adequate follow-up days) and/or subjects who experience the event. The numerator will be based on number of subjects-level events within the protocol-defined upper window. Subject-level events beyond the upper window will be counted as next visit.

Follow-up Visit	Protocol Defined Lower Window	Protocol Defined Upper Window
1 Month ¹	23	37
6 Months	152	212
12 Months	335	395

¹All events with 1-month window will be collected. However for the primary safety endpoint, events up to 30 days post-procedure will be included.

5.10.2 Event Rates Presented Using Exact Days Cut-Off System

The denominator will be based on number of subjects who reach the protocol-defined lower window (i.e. adequate follow-up days) and/or subjects who experience the event. The numerator will be based on number of subjects-level events within the exact desired cut-off days. Subject-level events beyond the exact cut-off days will be counted as next cut-off days.

For the primary safety endpoints, the analysis will be performed with the exact days (i.e. events up to 30 days).

Follow-Up Cut-Off	Days for Adequate Follow-Up	Maximum Days to Event
30 Days ¹	23	30
182 Days	152	182
365 Days	335	365

¹All events with 1-month window will be collected. However for the primary safety endpoint, events up to 30 days post-procedure will be included.

5.10.3 Missing Event Dates Considerations

All event rates will be calculated relative to the date of procedure (i.e. post-procedure).

When calculating rates of adverse events with missing event date (i.e. mm/dd/yyyy), the ideal is to work with safety and/or data management representatives to query sites for missing data. However missing and partial missing dates may be handled as using the worst case scenario as follows:

Partial Date Description	Action Taken
Entire onset date is missing	The procedure date will be used for the onset date.
The month and the day of the month are missing but the year is available	January 1 st will be used for the month and day of the onset date. However, if the imputed date falls before the procedure date, then the procedure date will be used for the onset date.
Day is missing, but the month and year are available	The 1 st will be used as the day of the onset date. However, if the imputed date falls before the procedure date, then the procedure date will be used for the onset date.

5.11 **Analysis of Site-Reported Serious and Non-Serious Adverse Events**

Subject-level event rates will be calculated at various time points (e.g. exact days) based on all events reported by the site regardless of whether or not they are ultimately adjudicated to be (or lead to) a MAE. These safety parameters will be summarized using descriptive statistics.

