#### **10.8. 30-Day Follow-up (+/- 7 days)**

30-day follow-up is an in-person interview. The following data will be collected:

- ABI measurements
- Rutherford category assessment
- Medication assessment
- Adverse events (any ongoing adverse events will be managed and treated by treating physicians per standard of care.)

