3.1.5 Worst Case Assessment for Safety

The PG of 88% will only allow 1 subjects with 30-day MAE out of 50 subjects treated with Jetstream. That is, the observed 30-day MAE-free rate in Jetstream will need to be at least 98% (49/50) in order to claim safety PG.

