5.2 Interim Analyses

Primary Endpoint report should include all enrolled 72 subjects in 1 month data as the enrollment could not be completed as plan of all the subjects. The BSC study team internally decided to add an interim analysis to care about the subject's safety, not only include Primary Endpoint and show all data that includes 6 month and 12 month in the PE report.

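### The missing-date fallback in SAP 5.10.3 has no floor at the last event-free visit, so it can place a late event at an early date that the trial's own visits contradict

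*SAP*

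**What the plan says.** SAP 5.10.3 names site queries as the ideal route to a missing date and then gives a fallback: "However missing and partial missing dates may be handled as using the worst case scenario as follows". The fallback has three rows:

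- Whole date missing: "The procedure date will be used for the onset date".
- Only the year known: "January 1 st will be used for the month and day of the onset date".
- Only the day missing: "The 1 st will be used as the day of the onset date".

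The two partial-date rows share one lower limit: "if the imputed date falls before the procedure date, then the procedure date will be used for the onset date". No row refers to a visit.

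The rule sits within SAP 5.10, which governs CEC-adjudicated events and MAE rates. SAP 5.10.2 counts primary safety events up to day 30 exactly. SAP 3.1.5 says the performance goal of 88% "will only allow 1 subjects with 30-day MAE out of 50 subjects treated with Jetstream".

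On visits, Protocol 10.8 states that "30-day follow-up is an in-person interview", with a window of 7 days either side, and it collects adverse events. Protocol 10.9 and 10.10 do the same at 6 and 12 months, within 30 days either side. SAP 5.2 plans to "show all data that includes 6 month and 12 month in the PE report", so events reported late can be in the database when the 30-day result is reported.

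**The concern.** A worst case should be the least favourable value that the data still allow. This rule can go beyond that. Take a subject with clean 30-day (on or after day 30) and 6-month visits who reports a TLR at 12 months without a usable date. The TLR is set to day 0. It then counts as a 30-day MAE and as an MAE within 24 hours, which makes the subject a procedural failure under Protocol 6.2.2 and SAP 5.12.

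Two results are exposed. The site-reported AE rates of SAP 5.11 are drawn from all AEs, including minor ones with weaker documentation, and undated late events would inflate the early time points. The primary safety test has room for only one or two events, so a single false one matters if it occurs. Late TLRs are to be expected: Protocol 4.2.1 reports clinically driven TLR in 26% (42/162) at 12 months in the Pathway PVD study. Whether any of them would be undated is a separate question, which the documents do not answer.

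**Working it through.** **1. Reproduce the plan's event limit.** Inputs: performance goal 0.88, one-sided alpha 0.025 and a normal-approximation test (SAP 3.1.3, 3.1.4). SAP 7.3 uses the standard error under the null hypothesis: Z = (p − 0.88) / √(0.88 × 0.12 / n), to be compared with 1.960.

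| n | MAEs | MAE-free | Z | one-sided p | result |
|---|---|---|---|---|---|
| 50 | 1 | 0.980 | 0.100/0.0460 = 2.176 | 0.0148 | pass |
| 50 | 2 | 0.960 | 0.080/0.0460 = 1.741 | 0.0409 | fail |
| 56 | 2 | 0.964 | 1.941 | 0.0261 | fail |
| 57 | 2 | 0.965 | 1.973 | 0.0243 | pass |
| 60 | 2 | 0.967 | 2.066 | 0.0194 | pass |
| 60 | 3 | 0.950 | 1.669 | 0.0476 | fail |

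The first row matches SAP 7.3 (Z = 2.1760, p = 0.0148). The limit is one event at 50 subjects and two from 57 to at least 60.

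**2. Apply the date rule to examples.**

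- Procedure 10 March, event 26 September of the same year (true day 200). Whole date missing: day 0. Year only: 1 January precedes the procedure, so day 0. Day missing: 1 September, day 175, which does no harm.
- Procedure 15 June, event 28 July (true day 43). Day missing: 1 July, day 16, counted as a 30-day event.

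**3. Share of late events moved into days 0–30.** Every procedure date over four years was combined with every true event day, evenly weighted. The even weighting is an assumption.

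| Known part of the date | true days 31–60 | 61–182 | 183–365 |
|---|---|---|---|
| nothing | 100% | 100% | 100% |
| year | 96% | 75% | 33% |
| month and year | 49% | 0% | 0% |

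These are shares of late events whose date is incomplete in that way. They are not shares of all events.

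**4. How much a visit floor removes.** Only an event-free visit on or after day 30 excludes a 30-day event. The 30-day visit may fall on days 23–37. Assume it is spread evenly over those 15 days. For a missing day and true days 31–61 (procedure dates over one year), the share moved into 30 days is 47.5% under the present rule. A floor at that visit lowers it to 27.6%. The rest stays, because a visit on days 23–29, or one after the event, does not contradict an early date.

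**5. Conditional effect on the primary test.** Take the SAP's expected MAE-free rate of 99%. With k false events among n subjects and a limit of c, the test passes if the other n − k subjects have at most c − k true events.

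- n = 50, c = 1, no false event: 0.99^50 + 50 × 0.01 × 0.99^49 = 0.605 + 0.306 = 0.911.
- n = 50, one false event: 0.99^49 = 0.611. Two false events: 0.
- n = 60, c = 2: 0.978 with none, 0.882 with one, 0.558 with two and 0 with three.

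**The case against.** The case for leaving the rule alone is substantial.

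- **It is a fallback.** Queries come first, the wording is permissive, and the SAP calls the rule worst case. This stands. A reader might infer that the plan always forces undated events to day 0. It does not, though permissive wording in an open single-arm trial also leaves a choice to be made after the data are seen.
- **An undated MAE should be rare.** Serious events are reported within 24 hours of awareness, source documentation is required and the AE form carries a date (Protocol 19.4). The CEC reviews a dossier for every death, major amputation and TLR (Protocol 21.3). Angiograms from any repeat procedure on the target vessel go to the core laboratory (SAP 5.7). This stands, and it is why the firmer gain lies in the SAP 5.11 rates.
- **It is conservative.** This stands: the rule can only add early events. A false failure would still be a wrong result.
- **Visits collect adverse events, not a positive record of being event-free.** This stands in part. The floor infers absence from a completed AE assessment, which could miss a procedure done elsewhere. That is a reason to keep the unbounded rule as a sensitivity analysis.

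Two stronger readings are tempting. One is that the trial loses a stated amount of power. That needs a rate of undated MAEs, and the documents give none. The other is that two MAEs always fail the safety test. Under the z test two pass from 57 subjects, and the 15% attrition is a maximum (Protocol 9.3). The Wald limit that SAP 7.3 also prints would be 0.906 at 48/50, above 88%.

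**Conclusion.** The gap is real: a stated rule can produce an onset date that a later in-person visit excludes. This happens whenever the whole date is missing, or only the procedure year is known, and a clean visit took place on or after day 30. The direction is against the device, so a false safety success cannot result.

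The effect on early site-reported AE rates is upward, with a size that depends on how many dates stay incomplete. The effect on the primary test is probably small, because MAE dates should be recoverable from source documents and CEC review; if all are recovered, it is nil. If one is not, the loss at a 1% true MAE rate is 0.911 to 0.611 at 50 subjects, or 0.978 to 0.882 at 60. These figures are conditional on one false event and are not an expected loss. A visit floor corrects only dates that a visit contradicts, so some reclassification remains when the 30-day visit falls on days 23–29.

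**What to change.** In SAP 5.10.3, keep the earliest-date imputation and add one sentence: the imputed date will not be earlier than the day after the last visit or contact at which the subject was documented free of that event or, for a death, last known alive. Report the present unbounded rule as a labelled worst-case sensitivity analysis.

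The cost is that sentence and a lookup of visit dates already in the database. The downside is that the main rule becomes slightly less conservative, which the sensitivity analysis makes visible.

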5.12 Technical and Procedural Successes

Technical success is defined as delivery and deployment of the assigned study stent to the target lesion to achieve residual angiographic stenosis no greater than 30% assessed visually.

Procedural success is defined as technical success with no MAEs noted within 24 hours of the index procedure. The procedural success is included in the protocol-defined additional assessments.

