### **7.5. Treatment**

All enrolled subjects will receive treatment with the investigational Jetstream System. Pre-dilation of target lesion is prohibited prior to the treatment of Jetstream System. After target lesion is adequately treated by the Jetstream System, PTA and/or stenting with commercially-available device(s) are allowed for optimizing treatment.

The investigator selects the size of Jetstream Catheter according to the proximal and distal reference vessel diameters

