### **Procedural recommendations:**

- Optimal target lesion/vessel treatment is recommended.
- Bailout stenting with a commercially-available stent or by-pass surgery may be performed at the discretion of operating physician, if the attempts with PTA have resulted any of the following:
  - Final residual stenosis at the target lesion being > 30% by visual assessment
  - Occurrence of Grade C or greater dissection (NHLBI)
  - Occurrence of clinically apparent perforation requiring treatments
  - Occurrence of any obstructive complication (e.g., recoil) demonstrating a marked decrease in the flow in the target vessel
- Angiographic complications, such as distal embolism or no reflow, should also be treated per standard practice. All angiographic complications during procedure should be documented by angiography and submitted to the Angiographic Core Laboratory for analysis.

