**Table 25.2-1: Definitions**

Term	Definition
TRANSATLANTIC INTER-SOCIETAL CONSENSUS (TASC) LESION GUIDELINES FOR FEMOROPOPLITEAL LESIONS	
Type A lesion:
 
 
• Single stenosis <math>\leq</math> 10 cm in length.
 
• Single occlusion <math>\leq</math> 5 cm in length.
 
 
Type B lesion:
 
 
• Multiple lesions (stenoses or occlusions), each <math>\leq</math> 5 cm
 
• Single stenosis or occlusion <math>\leq</math> 15cm not involving the infrageniculate popliteal artery
 
• Single or multiple lesions in the absence of continuous tibial vessels to improve inflow for a distal bypass
 
• Heavily calcified occlusion <math>\leq</math> 5cm in length
 
• Single popliteal stenosis
 
 
Type C lesion:
 
 
• Multiple stenoses or occlusions totaling <math>></math> 15 cm with or without heavy calcification
 
• Recurrent stenoses or occlusions that need treatment after two endovascular interventions
 
 
Type D lesion:
 
 
• Chronic total occlusions of the CFA or SFA (<math>></math> 20 cm, involving the popliteal artery)
 
• Chronic total occlusion of the popliteal artery and proximal trifurcation vessels
 

TECHNICAL SUCCESS	
Technical success is defined as <math>\leq</math> 30% residual angiographic stenosis in 2 near-orthogonal projections by visual assessment, after successfully debulking the target lesion and adjunctive interventions (such as percutaneous transluminal angioplasty/stenting).

THROMBUS (ANGIOGRAPHIC)	
Discrete, mobile intraluminal filling with defined borders with/without associated contrast straining; these are classified as either absent or present.

TOTAL OCCLUSION	
Lesion with no flow; implies 100% diameter stenosis.

VASCULAR COMPLICATION	
An occurrence of hematoma <math>></math> 5 cm, pseudoaneurysm, arteriovenous (AV) fistula, or need for vascular surgical repair.

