Additional Endpoints	
 • Procedural success, defined as $\leq 30\%$ residual angiographic stenosis in 2 near-orthogonal projections by visual assessment, after successfully debulking the target lesion and adjunctive interventions (such as percutaneous transluminal angioplasty/stenting) without any MAE within 24 hours post index procedure • Primary vessel patency of the treated segment assessed by duplex ultrasound sonography (DUS) at 6 and 12 months post-procedure without TLR* • Clinical success rate (defined as improved Rutherford classification by at least +1 class compared to baseline) at 30 days, 6 and 12 months • Hemodynamic success rate (defined as positive change in Ankle-Brachial Index) at 30 days, 6 and 12 months • MAE rate 6 and 12 months post-index procedure • All-cause death at 30 days, 6 and 12 months • Clinically-driven TLR and TVR rate at 30 days, 6 and 12 months • Target limb major amputation at 30 days, 6 and 12 months • Rate of peri-procedural complications: 
 ➢ Perforation at treated segment ➢ Abrupt closure at treated segment (including dissection and thrombosis) ➢ Significant dissection (types C – F) at treated segment

**Prospective, non-randomized, multicenter clinical study of the JETSTREAM™
 Atherectomy System (Jetstream) in treatment of occlusive atherosclerotic lesions in the
 superficial femoral and/ or proximal popliteal arteries in Chinese patients
 (JETSTREAM CHINA)**

	
 ➤ Aneurysm at treated segment ➤ Distal embolization 
* Vessel patency is defined as freedom from more than 50% stenosis based on DUS peak systolic velocity ratio comparing data within the treated segment to the proximal normal arterial segment. A systolic velocity ratio > 2.4 suggests > 50% stenosis.

Method of Assigning Subjects to Treatment	Once a subject signs the Ethics Committee-approved Informed Consent Form, and has met all inclusion criteria and has no exclusion criteria, they are eligible to be enrolled in the clinical study. All eligible subjects will be considered to receive treatment with the Jetstream System. Enrollment occurs at the time of advancement of the Jetstream catheter into the introducer sheath.

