5.8 Duplex Ultrasound

Duplex Ultrasound (DUS) assessments will be performed at 6 months (182 ± 30 days) and 12 months (365 ± 30 days) post-index procedure. Only records obtained during the clinical visit window will be selected for analysis unless the Biostatistics personnel are informed otherwise. In the case where multiple examinations are performed during the visit window, the best interpretable record will be selected. Measurements from DUS assessments that occur after a TLR will not be excluded from selection, but rather, endpoint definitions will appropriately account for the presence or absence of a prior TLR. Therefore a prior TLR may suggest a primary patency failure regardless of DUS result(s).

In the determination of $>50\%$ stenosis, a $PSVR > 2.4$ is used for the primary assessment. However a $PSVR > 2.0$ (e.g. alternative definition of vessel patency in SuperNOVA; BMS) and/or $PSVR > 2.5$ (e.g. definition of vessel patency in MAJESTIC; DES) and/or other clinical recommendation may be used in post-hoc analyses for publication purpose

The primary patency (binary rates) will be calculated based on the subjects who have adequate follow-up and/or have DUS assessments. The denominator will be based on number of subjects who reach the protocol-defined lower window and/or have events. The numerator will be based on number of subjects who finish the scheduled assessments (i.e. success or failure) within the protocol-defined upper window.

Follow-up Visit	Protocol Defined Lower ¹ Window for Assessment	Protocol Defined Upper Window for Assessment
6 Months	152	212
12 Months	335	395

¹Days for adequate follow-up

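### SAP 5.12 defines technical success by a study stent the trial does not have, and the SAP 5.8 patency numerator counts finished assessments rather than patent subjects

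*SAP*

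**What the plan says.** **Technical and procedural success.** SAP 5.12 begins: "Technical success is defined as delivery and deployment of the assigned study stent to the target lesion", and adds a visually assessed residual stenosis of at most 30%. It then defines procedural success as technical success with no MAE in the first 24 hours, and notes that procedural success is one of the protocol's additional assessments.

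The synopses of both documents give the test device as the Jetstream console and catheter. Stents enter only after atherectomy. Protocol 7.5 says "PTA and/or stenting with commercially-available device(s) are allowed for optimizing treatment". Protocol 10.6.1 says "Bailout stenting with a commercially-available stent or by-pass surgery may be performed at the discretion of operating physician" when angioplasty has left one of the listed problems.

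The SAP synopsis defines procedural success without any study stent: at most 30% residual stenosis in two projections, "after successfully debulking the target lesion and adjunctive interventions (such as percutaneous transluminal angioplasty/stenting) without any MAE within 24 hours post index procedure". SAP 5.1 and Protocol 6.2.2 agree with it. Protocol Table 25.2-1 gives the same content, without the 24-hour MAE condition, as technical success.

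**Primary patency.** SAP 5.8 describes the binary rate in three sentences. The first, a lead-in, limits the rate to subjects with enough follow-up or a scan. The second sets out who is in the denominator: "The denominator will be based on number of subjects who reach the protocol-defined lower window and/or have events". The third turns to the other half of the fraction and reads: "The numerator will be based on number of subjects who finish the scheduled assessments (i.e. success or failure) within the protocol-defined upper window". The windows are days 152 to 212 and days 335 to 395. SAP 5.1 defines patency as freedom from more than 50% stenosis on duplex ultrasound. SAP 7.1 derives a subject as patent at 12 months only if the scan was done with a velocity ratio of 2.4 or less and there was no earlier clinically-driven TLR and no earlier bypass. It does not mention 6 months.

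**The concern.** Each rule, followed as written, returns a number that is not the endpoint it is labelled with. No subject can receive an assigned study stent, so 5.12 yields no successes. A numerator that takes in failures as well as successes measures how many scans were completed, not how many vessels stayed open.

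SAP 5.15, 6 and 7 give all programming and validation to an independent CRO, which works from this text. Procedural success goes into both the 30-day and the 12-month report (SAP 5.1). Patency goes into the 12-month report, and SAP 5.2 also brings 6- and 12-month data into the primary endpoint report. If the SAP holds conflicting rules, the programmer has to choose between them after data exist, when the plan should already have settled it.

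**Working it through.** The plan states no figure for either endpoint, so there is nothing to reproduce. The check compares definitions and then illustrates the size.

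**1. Technical success, side by side**

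| Element | SAP 5.12 | Protocol Table 25.2-1 |
|---|---|---|
| Device step | Assigned study stent delivered and deployed | Target lesion debulked, then adjunctive treatment |
| Residual stenosis | 30% or less, visual | 30% or less, visual |
| Projections | Not stated | Two, near-orthogonal |

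The device step is the contradiction. It also removes debulking, which is what the test device does. Protocol Table 25.2-1 builds procedural success on technical success in the same way as 5.12, so only the technical success sentence is wrong; procedural success inherits the error.

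Literal result in the 60-subject primary cohort (Protocol 11.1.1.2): subjects with an assigned study stent = 0, so the rate is 0/60 = 0%.

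**2. Patency, general form.** Let D be the 5.8 denominator (subjects who reach the lower window and/or have events), m the number who finish the assessment in the window, and k the number patent under 7.1.

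- Literal 5.8 rate = m/D. It does not contain k.
- Patency rate = k/D.
- Difference = (m − k)/D, the share of D that was assessed and found not patent.

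Under 7.1 a patent subject must have a scan, so k ≤ m. The literal rate is therefore never below the patency rate, and equals it only if every assessed subject is patent.

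**3. Patency, illustration.** Assumed: D = 60 and m = 51 (85% scanned).

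| k patent | Literal 5.8 | k/60 |
|---|---|---|
| 20 | 51/60 = 85.0% | 33.3% |
| 32 | 51/60 = 85.0% | 53.3% |
| 45 | 51/60 = 85.0% | 75.0% |

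The middle value is 61.8% of 51 = 31.5, rounded to 32. The 61.8% is the lesion-level 12-month patency reported for the historical study in Protocol 4.2.1, used only to choose a count.

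Varying completion, with 61.8% of those assessed taken as patent and rounded:

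| m | k | Literal m/60 | k/60 | Difference (points) |
|---|---|---|---|---|
| 48 | 30 | 80.0% | 50.0% | 30.0 |
| 51 | 32 | 85.0% | 53.3% | 31.7 |
| 54 | 33 | 90.0% | 55.0% | 35.0 |
| 60 | 37 | 100.0% | 61.7% | 38.3 |

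On these assumptions better follow-up widens the error, because more non-patent subjects enter the literal numerator.

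**4. Comparison with the MAE rule.** SAP 5.10.1 uses a similar denominator, but its numerator names the outcome: subject-level events inside the upper window. In 5.8 the corresponding place names completion of the assessment.

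**The case against.** The best defence is that a competent programmer would not produce these numbers. The SAP states procedural success correctly in full twice, in the synopsis and in 5.1, and 5.1 is the section that lists what will be reported. Technical success is not itself a listed endpoint. For patency, 5.8 sets the velocity-ratio threshold, says a prior TLR may mean failure, and labels the result primary patency. Its numerator sentence may be a loose way of saying that the outcome must be known by the upper window. SAP 7.1 then supplies a usable subject-level rule.

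This lowers the likelihood of a wrong output, and it means the repair is one of drafting. It does not remove the conflict. SAP 5.12 is the section devoted to these two successes, and 5.8 is the only section that says how the binary patency rate is formed. A plan should not depend on the programmer setting aside its own rule.

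Three stronger readings are tempting and should be resisted:

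- A reader might infer that 5.8 has two competing denominators. Its table footnote equates the lower window with adequate follow-up, so the lead-in and the rule largely coincide. The explicit sentence (lower window and/or events) can stand.
- A reader might infer that subjects without a scan have no rule at all. SAP 7.1 requires the scan to be done before a subject can be patent, so at 12 months such a subject stays in the denominator and out of the numerator. What is missing is an outright statement and the 6-month case.
- A reader might apply the literal rule to the historical study's 123 lesions, or treat its 7% stenting rate as a ceiling on success. Neither works: 123 is that study's reported patency denominator, not the number reaching a window, and the 7% counts subjects while its residual-stenosis result counts lesions.

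**Conclusion.** The point holds for two rules. SAP 5.12 makes a listed endpoint depend on a device that is not in the trial, which gives 0% if followed literally. The SAP 5.8 numerator gives a completion proportion: 85.0% instead of 53.3% in the central illustration, a difference of 31.7 points. That size rests on assumed values (60 in the window, 51 scanned, 32 patent) and is not a forecast. The direction does not depend on them: the literal patency figure can only equal or exceed the true one.

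A reader might infer that the study's success decision is at risk. It is not. Both endpoints are additional and observational, with no formal test (SAP 5.1). The 30-day MAE test, the stenosis-reduction test, alpha and the sample size are unaffected. The documents also do not show that a wrong figure will be reported, only that the plan as written permits one. The correction should be made before programming.

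**What to change.** - **SAP 5.12:** replace the technical success sentence with the definition in Protocol Table 25.2-1. The procedural success sentence can then stay.
- **SAP 5.8:** set the numerator to subjects derived as patent under 7.1, and keep the stated denominator of subjects who reach the lower window and/or have events.
- **SAP 7.1:** state that the derivation applies at both 6 and 12 months, and say outright that a subject in the denominator without an in-window scan is not counted as patent.
- **Patency table:** report the number of such subjects at each visit. In the illustration this is 60 − 51 = 9, which lets a reader also form 32/51 = 62.7%.

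The cost is wording in three SAP sections and one extra count per visit, in a SAP amendment approved before the analysis as SAP 5.16 provides. It needs no new data, no protocol change and no change to the primary analyses. The reported patency rate may be lower than the literal 5.8 figure.
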